| No Exercise + Atorvastatin | 24 |
| No Exercise + Placebo | 24 |

Randomization is stratified by:

1. Sex (male/female)
2. Prior active statin treatment (yes/no)

Block sizes are concealed from investigators. Randomization codes are securely stored and revealed only after database lock.

11. Sample size calculations

Sample-size calculations were prespecified for the primary mechanistic contrast (Exercise + Placebo vs Exercise + Atorvastatin) for the primary endpoint (Δ CS) and the key secondary endpoint (Δ VO_{2peak}).

Power calculations (as prespecified in the published protocol) used prior training data (Sjúrðarson *et al.*, 2022a, 2022b): mean $\Delta\text{CS} \approx 25 \mu\text{mol}\cdot\text{g}^{-1}\cdot\text{min}^{-1}$, SD $\approx 18 \mu\text{mol}\cdot\text{g}^{-1}\cdot\text{min}^{-1}$, and a target between-group difference of $17 \mu\text{mol}\cdot\text{g}^{-1}\cdot\text{min}^{-1}$, consistent with attenuation magnitudes reported previously (Mikus *et al.*, 2013). For $\text{VO}_{2\text{peak}}$, we assumed $\Delta \approx 3.6 \pm 3.3 \text{ mL}\cdot\text{kg}^{-1}\cdot\text{min}^{-1}$ and targeted a $3.0 \text{ mL}\cdot\text{kg}^{-1}\cdot\text{min}^{-1}$ between-group difference.

Final enrolled sample size.

A total of $N = 120$ participants were randomized (36 per exercise arm; 24 per non-exercise arm). The primary mechanistic comparison—Exercise + Placebo vs Exercise + Atorvastatin—is effectively a two-group contrast, and power calculations were therefore based on the two exercise groups.

Using the effect-size assumptions prespecified in the published protocol, the achieved sample provides:

- **Citrate synthase (CS) activity:**
 - With full enrollment ($n = 36$ per group), power is approximately 97–98% to detect a $17 \mu\text{mol}\cdot\text{g}^{-1}\cdot\text{min}^{-1}$ difference (SD ≈ 18).
 - With 10% attrition (≈ 33 per group), power remains high at ≈ 94 –95%.

- **$\text{VO}_{2\text{peak}}$:**
 - With full enrollment ($n = 36$ per group), power is approximately 96–97% to detect a $3.0 \text{ mL}\cdot\text{kg}^{-1}\cdot\text{min}^{-1}$ difference (SD ≈ 3.3).
 - With 10% attrition (≈ 33 per group), power remains ≈ 93 –95%.

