Power calculations were performed in G*Power (version 3.1.9.7) using a two-sample, two-sided t-test with $\alpha = 0.05$, assuming equal group sizes for the exercise arms. Power calculations are based on a two-sample t-test approximation for the primary exercise-arm contrast; the primary analysis will use a constrained mixed model, which is expected to provide similar or greater efficiency under the repeated-measures structure.

Interpretation note (pre-specified).

Because (i) a clinically meaningful CS difference is not firmly established and (ii) assay units/conditions vary across studies, true between-group differences smaller than $17 \mu\text{mol}\cdot\text{g}^{-1}\cdot\text{min}^{-1}$ may still be clinically relevant.

For $\text{VO}_{2\text{peak}}$, relatively small differences may also be clinically meaningful. While meta-analytic evidence indicates that each 1-MET ($\approx 3.5 \text{ mL}\cdot\text{kg}^{-1}\cdot\text{min}^{-1}$) higher cardiorespiratory fitness is associated with substantially lower all-cause and cardiovascular mortality risk (Myers *et al.*, 2002; Kodama *et al.*, 2009), prospective cohorts with directly measured $\text{VO}_{2\text{peak}}/\text{VO}_{2\text{max}}$ also demonstrate prognostic gradients per $\sim 1 \text{ mL}\cdot\text{kg}^{-1}\cdot\text{min}^{-1}$, implying that differences on the order of $\sim 2 \text{ mL}\cdot\text{kg}^{-1}\cdot\text{min}^{-1}$ are clinically meaningful (Keteyian *et al.*, 2008; Laukkanen *et al.*, 2016; Khan *et al.*, 2018; Tari *et al.*, 2024). Accordingly, a between-group difference of $\sim 2.0 \text{ mL}\cdot\text{kg}^{-1}\cdot\text{min}^{-1}$ (≈ 0.6 MET) can be considered a clinically relevant difference in $\text{VO}_{2\text{peak}}$.

With 120 randomized participants, the study has approximately 80% power to detect between-group differences of $\sim 12 \mu\text{mol}\cdot\text{g}^{-1}\cdot\text{min}^{-1}$ in CS activity and $\sim 2.1 \text{ mL}\cdot\text{kg}^{-1}\cdot\text{min}^{-1}$ in $\text{VO}_{2\text{peak}}$.

12. Framework

Analyses will follow a superiority framework. For the primary endpoint (change in CS activity), all four groups will be compared with each other (six pre-specified pairwise contrasts). Multiplicity across the six tests will be controlled using the Holm–Šidák procedure, maintaining a familywise two-sided $\alpha = 0.05$. Superiority will be claimed only for contrasts meeting this adjusted criterion.

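### Section 11 credits 80% power at ~12 (CS) and ~2.1 (VO2peak) to all 120 participants; the CS figure fits only the 36 vs 36 exercise contrast, and the VO2peak figure is slightly low even there

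*SAP*

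**What the plan says.** SAP Section 11 closes its Interpretation note, which is marked as pre-specified, with "With 120 randomized participants, the study has approximately 80% power to detect between-group differences of" about 12 µmol/g/min for CS and about 2.1 mL/kg/min for VO2peak. The sentence gives no contrast, group size, loss or significance level.

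Earlier in the section the scope is narrower. The trial's "participants were randomized (36 per exercise arm; 24 per non-exercise arm"), and "power calculations were therefore based on the two exercise groups". The method is a two-sample, two-sided t-test at 0.05 with equal exercise arms. The SDs of change are 18 for CS, taken from earlier training data, and 3.3 for VO2peak. Power for the targets of 17 and 3.0 is given at 36 per group and again at about 33 per group, after 10% attrition.

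Section 12 then states that for the primary endpoint "all four groups will be compared with each other (six pre-specified pairwise contrasts"), with Holm–Šidák control, and that any contrast meeting the adjusted criterion may support a superiority claim. By the arm sizes in Section 10, contrast 1 in Section 12.1 is 36 vs 36, contrasts 2 to 5 are 36 vs 24, and contrast 6 is 24 vs 24.

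**The concern.** The sentence attaches a power figure to the whole trial and to between-group differences without restriction. The figure comes from 72 of the 120 participants, with every follow-up value observed. The attainment bullets earlier in Section 11 each carry an n per group and a loss case; this sentence carries neither and puts the trial total in their place.

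It sits just before a section that makes six contrasts confirmatory for CS, five of which involve at least one arm of 24. The SAP gives no power for those five, so this sentence is the only one a reader could apply to them. Contrast 6, statin alone against no intervention, is the most exposed: it has the smallest arms and no target difference of its own. A non-significant result there, read against 80% power for 12 units, could look more informative than the arm sizes allow.

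**Working it through.** **Inputs, all from SAP Sections 10 to 12:** arms of 36, 36, 24 and 24; SD of change 18 (CS) and 3.3 (VO2peak); two-sided alpha 0.05; two-sample t-test; stated differences 12 and 2.1; 10% attrition, about 33 per exercise arm.

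**Formula.** SE = SD × √(1/n1 + 1/n2); noncentrality = difference / SE; df = n1 + n2 − 2. Power is the probability that a noncentral t variable falls outside ± the two-sided 5% critical value.

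**Step 1: reproduce the CS figure.** For 36 vs 36, SE = 18 × √(2/36) = 4.243, noncentrality = 12/4.243 = 2.828, df = 70, critical value 1.994, power **79.7%**. Power of 80% is reached at 12.05 units. The SAP's ~12 is therefore reproduced for this contrast without loss. Splitting all 120 participants gives 94.4% (72 vs 48) or 95.2% (60 vs 60), so the figure does not come from the full sample.

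**Step 2: the VO2peak figure for the same contrast.** SE = 3.3 × √(2/36) = 0.778, noncentrality = 2.1/0.778 = 2.700, power **75.9%**. The difference needed for 80% is 12.05/18 × 3.3 = 2.21. The standardised differences show the mismatch: 12/18 = 0.667 against 2.1/3.3 = 0.636.

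**Step 3: 10% loss in the exercise contrast (33 vs 33).** Power at 12 is 76.0%. Power of 80% needs 12.60 in CS, and 12.60/18 × 3.3 = 2.31 in VO2peak.

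**Step 4: the other five CS contrasts.** This step assumes that SD 18 holds in every arm, and uses unadjusted 0.05. The loss column applies the same 10% to the arms of 24, giving about 22, which is also an assumption.

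| Contrast type | SE | Noncentrality at 12 | Power at 12, no loss | Difference for 80%, no loss | Power at 12, 10% loss |
|---|---|---|---|---|---|
| 36 vs 36 (contrast 1) | 4.243 | 2.828 | 79.7% | 12.05 | 76.0% |
| 36 vs 24 (contrasts 2–5) | 4.743 | 2.530 | 70.1% | 13.51 | 66.2% |
| 24 vs 24 (contrast 6) | 5.196 | 2.309 | 61.8% | 14.87 | 57.9% |

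**Step 5: sensitivity to the SD assumption.** The SAP gives no SD of change for untrained arms. Illustrative values, not from the SAP, with SD 18 kept in the exercise arm:

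- Non-exercise SD 15: 36 vs 24 has SE = √(18²/36 + 15²/24) = 4.287 and power about 79–80%; 24 vs 24 has SE = 15 × √(2/24) = 4.330 and power about 77%.
- Non-exercise SD 12: SE 3.873 and power about 86–87%; SE 3.464 and power about 92%.

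The two-figure ranges are the t and normal approximations.

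**Step 6: the alpha used.** These figures use unadjusted 0.05, which is the most favourable Holm–Šidák step. At the first step, 1 − 0.95^(1/6) = 0.0085, power at 12 with SD 18 and no loss is 55.1%, 43.0% and 34.2% for the three contrast types. This is why the sentence should state its alpha.

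**The case against.** The strongest defence is that the scope is already on the page. Section 11 opens by tying its calculations to the primary mechanistic contrast, repeats that they rest on the two exercise arms, and says so again for the t-test approximation shortly before the note. The note itself discusses differences below 17, the target for that contrast. Read in context, ~12 is the sensitivity of that contrast, and it is correct. This stands: a reader might infer a CS arithmetic error, and the document does not support that.

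A reader might also infer that the other five contrasts simply have 62–70% power. The document does not support that either. SD 18 comes from people who trained, and step 5 shows that a smaller SD in untrained arms could bring power at 12 close to or above 80%. Section 11 also expects the constrained mixed model to be at least about as efficient as the t-test, although it gives no correlation from which to quantify a gain.

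Nor does it follow that the smaller contrasts are inadequate for their purpose. Twelve units is not a design target for any of them. If untrained change were near zero (an assumption), the SAP's training effect of about 25 units would give 36 vs 24 a power of about 99.9% at 0.05. Confidence intervals are planned for every contrast, and no decision rule uses this sentence.

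On losses, the word randomized can fairly be taken to mean full enrolment, and the shift for contrast 1 is small (12.05 to 12.60). VO2peak is outside the confirmatory family, so its figures for the other contrasts are optional.

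What remains is that the sentence names the whole trial and no contrast, and that its VO2peak value does not reach 80% under the SAP's own inputs even for the contrast it was computed for.

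**Conclusion.** The point holds as a misstatement of scope plus a small numerical slip for VO2peak. About 80% power at ~12 in CS is correct for Exercise + Placebo vs Exercise + Atorvastatin only, at 36 vs 36, no loss and unadjusted two-sided 0.05. For that same contrast, 2.1 in VO2peak gives 75.9%, about four points short, and about 2.2 is needed.

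For the five remaining CS contrasts the SAP states no power. The values of about 70% (36 vs 24) and 62% (24 vs 24) at 12 units are conditional on SD 18 in all arms, unadjusted alpha and no loss. A smaller SD in untrained arms would raise them; losses or an earlier Holm–Šidák step would lower them. The main practical consequence is for how a null result in contrast 6 is read. No planned estimate or test is affected.

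**What to change.** Replace the closing sentence of the Interpretation note with wording such as:

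> For Exercise + Placebo vs Exercise + Atorvastatin (36 vs 36, no loss, unadjusted two-sided 0.05), 80% power is reached at ~12 in CS and ~2.2 in VO2peak (~12.6 and ~2.3 with 10% loss). For CS, assuming SD 18 in all arms, the 36 vs 24 contrasts need ~13.5 and the 24 vs 24 contrast ~14.9, on the same alpha and without loss.

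Add that SD 18 derives from training data and that its use for the non-exercise arms is an assumption. Matching VO2peak values for the other contrasts are optional, because those tests are not confirmatory.

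The cost is a short rewording, and some stated figures become less favourable. Sample size, models and decision rules stay as they are.

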For all outcomes, we will report within-group estimated mean changes (V2–V1) and between-group differences in change (contrasts of V2–V1), each with 95% confidence intervals (CIs). Analyses will be two-sided and performed using $\alpha = 0.05$. Multiplicity will be controlled for the primary endpoint (six tests) using the Holm–Šidák procedure, maintaining a familywise two-sided $\alpha = 0.05$. For all other secondary and exploratory outcomes, confidence intervals and p-values will not be adjusted for multiple testing.

19–20. Adherence, Protocol Deviations, and Analysis Populations

Analysis Populations

Intention-to-Treat (ITT) – primary analysis set

All randomized participants will be included in the primary analyses and analyzed according to their allocated intervention group, irrespective of intervention initiation, adherence, or protocol deviations.

Per-Protocol (efficacy under adherence):

Participants without major protocol deviations who (i) complete V1 and V2 assessments and (ii) meet adherence criteria for their assigned intervention(s):

- Medication arms: $\geq 75\%$ of planned doses at assigned dose (80 mg; 40 mg if medically indicated).
- Exercise arms: $\geq 75\%$ session attendance and $\geq 75\%$ of prescribed high-intensity interval time performed at $\geq 90\%$ maximal aerobic power (MAP).

Adherence definitions and quantification

Medication adherence (%): (doses taken / doses planned) × 100; sources: medication logs + pill count.

Exercise adherence:

- **Session attendance (%):** (sessions attended / sessions prescribed) × 100 (3 sessions/week planned).
- **Intensity adherence (%):** (completed high-intensity interval time at ≥90% MAP / prescribed high-intensity interval time) × 100. MAP is defined as the lowest cycling power output eliciting VO_{2peak} during the incremental test. Primary source: power output; HR as backup. If session-level data are missing, within-participant imputation from temporally adjacent sessions in the same phase may be used.

Protocol Deviations

Major deviations include prohibited medications, <75% adherence to allocated medication/exercise criteria, withdrawal of consent, or non-attendance of V2 testing. All deviations will be listed and summarized by intervention group.

Section 5: Trial Population

21. Screening data

Screening and enrolment figures will be summarized in the CONSORT flow diagram.

Individual-level screening data will not be reported.

22. Eligibility criteria

Inclusion criteria:

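### Holm–Šidák on the six CS contrasts is valid, but a closed test over the logically possible null sets keeps every rejection and adds power at the same familywise 0.05

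*SAP*

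**What the plan says.** Section 12 sets six two-sided pairwise contrasts on the primary endpoint and fixes the adjustment: "Multiplicity across the six tests will be controlled using the Holm–Šidák procedure", at a familywise 0.05. It adds: "Superiority will be claimed only for contrasts meeting this adjusted criterion". Sections 16–18 repeat the rule: "Multiplicity will be controlled for the primary endpoint (six tests) using the Holm–Šidák procedure". The two places agree.

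Section 12.1 labels contrast 1 (Exercise + Placebo vs Exercise + Atorvastatin) as primary but gives it no priority in testing. It goes through the same step-down as the other five.

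Section 11 bases power on a "two-sample, two-sided t-test with $\alpha = 0.05$, assuming equal group sizes for the exercise arms", with 17 units as the target difference, SD 18, an expected training gain of 25, and arms of "36 per exercise arm; 24 per non-exercise arm".

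**The concern.** Holm–Šidák treats the six null hypotheses as if any subset of them could be true. For pairwise comparisons of four means that is impossible. If Exercise + Placebo equals both non-exercise arms, for example, those two arms must equal each other. Once any one pair differs, at most three of the other five nulls can still hold. Holm–Šidák nevertheless sets its second and third steps as if five and then four could.

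The level spent on impossible combinations could go to real ones without exceeding 0.05. What is at stake is some power on contrast 1, the question the trial was sized for, and on contrasts 4 and 5 (Exercise + Atorvastatin against each non-exercise arm). Section 11 itself says that differences below 17 may matter and quotes about 80% power near 12 units. At a difference of that size the choice of procedure affects more trials.

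**Working it through.** **Inputs.** From Section 11: 36/36/24/24 participants, SD of change 18, gain 25 in Exercise + Placebo, target difference 17 (so Exercise + Atorvastatin gains 25 − 17 = 8), and the 12-unit difference (25 − 12 = 13). Assumed: mean change 0 in both non-exercise arms, because the SAP gives no figure. Means are written in the order Exercise + Placebo / Exercise + Atorvastatin / No Exercise + Atorvastatin / No Exercise + Placebo.

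**The plan's own figure.** Noncentrality = 17 / (18 × √(2/36)) = 17 / 4.243 = 4.007 on 70 degrees of freedom. Two-sided power at 0.05 is 97.7%, which matches the stated 97–98%. This is unadjusted power.

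**Which nulls can be true together.** Using the numbering of Section 12.1, the possible sets are:
- six single contrasts;
- {1,6}, {2,5}, {3,4}, where two separate pairs are equal;
- {1,2,4}, {1,3,5}, {2,3,6}, {4,5,6}, where three arms are equal;
- all six, where all arms are equal.

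That makes 6 + 3 + 4 + 1 = 14, out of 2⁶ − 1 = 63 subsets.

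**Levels.** The Šidák level for m hypotheses is 1 − 0.95^(1/m): 0.0500 (m = 1), 0.0253 (2), 0.0170 (3), 0.0127 (4), 0.0102 (5), 0.0085 (6).

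**Why nothing is lost.** Holm–Šidák is the closed test over all 63 subsets at these levels. Keeping only 14 of them removes conditions and adds none, so every Holm–Šidák rejection stays.

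**What it means for contrast 1.** Suppose contrasts 2 and 3 are already rejected at 0.0085. The sets {1,2,4}, {1,3,5} and all six are then rejected too, and only {1} and {1,6} still protect contrast 1. It is tested at 0.0253. Holm–Šidák tests it at its third step, at 0.0127. Fixed divisors 6,3,3,3,2,1 would test it at 0.0170.

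**Power by simulation** (100,000 trials per scenario, t-tests on change with pooled SD):

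| Means | Contrast | Holm–Šidák | Closed test | Gain (points) |
|---|---|---|---|---|
| 25/8/0/0 | 1 | 94.1% | 95.9% | 1.8 |
| 25/8/0/0 | 4 and 5 | about 24.7% | 27.9% | 3.2 |
| 25/13/0/0 | 1 | 68.2% | 71.4% | 3.2 |
| 25/13/0/0 | 4 and 5 | about 64.2% | 70.6% | 6.4 |

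At least one of the six claims changes in about 9% of trials at 25/8/0/0 and 16% at 25/13/0/0. With 10% attrition (33/33/22/22) at 25/13/0/0, contrast 1 goes from 63.0% to 67.2% and contrasts 4 and 5 from 59.4% to 66.2%. At 12/0/0/0, contrast 1 goes from 58.4% to 62.9%.

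**Fixed divisors.** At 25/8/0/0 the 6,3,3,3,2,1 version takes contrast 1 from 94.0% only to 94.6%, and contrasts 4 and 5 up by about 0.2 points.

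**Error control.** With all means equal, familywise error is about 20% unadjusted and about 4.2% with Holm–Šidák. The closed test stayed at 5.0% or below, within Monte Carlo error, in every configuration. The highest was at 25/25/0/0, where Holm–Šidák is also close to 5%.

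**How much of the lost power returns.** At 25/8/0/0, contrast 1 loses 97.8 − 94.1 = 3.7 points to adjustment and regains 1.8. Contrasts 4 and 5 lose about 39 − 24.7 = 14.3 and regain 3.2. At the 12-unit difference, contrast 1 loses about 80 − 68.2 = 11.8 and regains 3.2.

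**The case against.** The strongest reply is that nothing here is wrong. Sections 12 and 16–18 agree, Holm–Šidák is a recognised prespecified procedure, and it holds the error rate it promises. That stands. A reader might infer that the plan has a multiplicity error; the documents do not support that.

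Three other inferences go too far.
- *Power is given up for nothing.* Adjusting at all brings familywise error from about 20% to about 4%. The closed test simply spends more of the permitted 5%: at 25/8/0/0 realised error is about 2.3% with Holm–Šidák and roughly 4% with the closed test.
- *Contrast 1 is usually tested at 0.0127.* It has the third-smallest p-value in 68% of trials at 25/8/0/0 but in only 40% at 25/13/0/0.
- *These are the SAP's own scenarios.* The two exercise means and the SD are; the two zeros are assumed.

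It is also fair to say that the gain on contrast 1 at the design difference is under 2 points where power is already high, that Section 11 sized the trial on the two exercise arms and not on contrasts 4 and 5, and that at 25/8/0/0 those two stay near 28% either way.

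Finally, the simulation used t-tests on change, not the constrained mixed model with Satterthwaite degrees of freedom of Section 27, so the power figures are approximate. The ordering of the two procedures does not depend on this: both work from the same six p-values, and the closed test at Šidák levels rejects whatever Holm–Šidák rejects. It relies on the same Šidák bound and needs no new assumption.

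**Conclusion.** This is an optional efficiency improvement to a valid plan. A procedure that is never worse exists at the same familywise level, with the same six contrasts and two-sided tests. Its benefit is about 2 points on contrast 1 at the 17-unit target and about 3 points at a 12-unit difference; for contrasts 4 and 5 it is about 3 and 6 points. These sizes rest on zero mean change in both non-exercise arms, SD 18 and full enrolment. More than half of the loss against unadjusted power remains in each case set out above, because it comes from adjusting for six tests at all, which is justified.

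**What to change.** In Sections 12 and 16–18, by a dated amendment before unblinding, replace the Holm–Šidák wording with a closed (subset-based) step-down test over the 14 logically possible null sets, using Šidák levels within each set. Apply it to the six p-values from the constrained mixed model with Satterthwaite degrees of freedom. The adjusted p-value for a contrast is the largest value of 1 − (1 − p_min)^m over the five sets that contain it, where m is the size of the set and p_min its smallest p-value. Listing the 14 sets in the SAP removes ambiguity.

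The correlation-using Westfall version is an alternative; the SAP would then need to say how the Satterthwaite degrees of freedom enter the joint distribution.

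Two near-variants should be ruled out by name. Fixed Shaffer divisors 6,3,3,3,2,1 give only about 0.6 points on contrast 1 at 25/8/0/0. Bonferroni levels can lose an occasional Holm–Šidák rejection, since 0.05/6 = 0.0083 is below 0.0085.

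The cost is a less familiar procedure to explain and a few lines of code in R, the software named in Section 31. No contrast loses power under the Šidák version. If the authors prefer to keep Holm–Šidák, the plan remains valid.

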12.1 Statistical Hypotheses

The primary mechanistic hypothesis is that supervised exercise training increases skeletal-muscle CS activity and that concomitant high-dose atorvastatin attenuates this response.

The key secondary hypothesis is that concomitant atorvastatin treatment attenuates training-induced improvements in cardiorespiratory fitness, assessed as the between-group difference in change in VO_{2peak} between Exercise + Placebo and Exercise + Atorvastatin.

For the primary endpoint (ΔCS), six pre-specified pairwise contrasts will be evaluated to characterize exercise, statin, and combined effects:

| No. | Comparison | Scientific question |
|-----|--|--|
| 1 | Exercise + Placebo > Exercise + Atorvastatin | Does atorvastatin blunt exercise-induced mitochondrial gains? (Primary contrast) |
| 2 | Exercise + Placebo > No Exercise + Atorvastatin | Benefit of exercise alone vs. drug alone |
| 3 | Exercise + Placebo > No Exercise + Placebo | Absolute effect of exercise training |
| 4 | Exercise + Atorvastatin > No Exercise + Atorvastatin | Can exercise mitigate potential statin-related attenuation? |
| 5 | Exercise + Atorvastatin > No Exercise + Placebo | Combined treatment vs. no intervention |
| 6 | No Exercise + Placebo > No Exercise + Atorvastatin | Do statins alone affect mitochondrial function? |

Contrasts are listed in the hypothesized direction for interpretation; all tests will be two-sided.

13. Statistical interim analyses and stopping guidance

No interim analyses for efficacy are planned. No early stopping guidelines were specified.

14. Timing of final analysis

Data collection is considered complete after the last participant's last visit. Analyses will begin only after:

1. all data have been entered and cleaned,
2. all queries have been resolved, and
3. The randomization code has been formally unblinded following database lock.

No unblinded interim looks are permitted before database lock.

15. Timing of outcome assessments

Primary and secondary outcomes are measured at V1 (baseline) and V2 (12 weeks). Blood samples and questionnaire data are collected at V1, week 6, and V2.

Section 4: Statistical principles

16–18. Confidence Intervals, P-values, and Multiplicity

For all outcomes, we will report within-group estimated mean changes (V2–V1) and between-group differences in change (contrasts of V2–V1), each with 95% confidence intervals (CIs). Analyses will be two-sided and performed using $\alpha = 0.05$. Multiplicity will be controlled for the primary endpoint (six tests) using the Holm–Šidák procedure, maintaining a familywise two-sided $\alpha = 0.05$. For all other secondary and exploratory outcomes, confidence intervals and p-values will not be adjusted for multiple testing.

19–20. Adherence, Protocol Deviations, and Analysis Populations

Analysis Populations

Intention-to-Treat (ITT) – primary analysis set

All randomized participants will be included in the primary analyses and analyzed according to their allocated intervention group, irrespective of intervention initiation, adherence, or protocol deviations.

Per-Protocol (efficacy under adherence):

Participants without major protocol deviations who (i) complete V1 and V2 assessments and (ii) meet adherence criteria for their assigned intervention(s):

- Medication arms: $\geq 75\%$ of planned doses at assigned dose (80 mg; 40 mg if medically indicated).
- Exercise arms: $\geq 75\%$ session attendance and $\geq 75\%$ of prescribed high-intensity interval time performed at $\geq 90\%$ maximal aerobic power (MAP).

Adherence definitions and quantification

Medication adherence (%): (doses taken / doses planned) × 100; sources: medication logs + pill count.

Exercise adherence:

- **Session attendance (%):** (sessions attended / sessions prescribed) × 100 (3 sessions/week planned).
- **Intensity adherence (%):** (completed high-intensity interval time at ≥90% MAP / prescribed high-intensity interval time) × 100. MAP is defined as the lowest cycling power output eliciting VO_{2peak} during the incremental test. Primary source: power output; HR as backup. If session-level data are missing, within-participant imputation from temporally adjacent sessions in the same phase may be used.

Protocol Deviations

Major deviations include prohibited medications, <75% adherence to allocated medication/exercise criteria, withdrawal of consent, or non-attendance of V2 testing. All deviations will be listed and summarized by intervention group.

Section 5: Trial Population

21. Screening data

Screening and enrolment figures will be summarized in the CONSORT flow diagram.

Individual-level screening data will not be reported.

22. Eligibility criteria

Inclusion criteria:

- Age: 40–65 years.
- LDL-C >4.0 mmol/L, calculated via the Friedewald equation ($LDLC = \text{Total Cholesterol} - (\text{HDL-C} + 0.45 \times \text{Triglycerides})$).

- Written informed consent provided prior to any study procedures.

Exclusion criteria:

- Diagnosed with serious chronic disease including type 1 or 2 diabetes.
- Cancer.
- A history of atherosclerotic cardiovascular disease.
- A history of major depression or other severe psychiatric disorders.
- Severe renal dysfunction (creatinine clearance <30 mL/min).
- Severe hepatic impairment, defined as alanine-aminotransferase $\geq 3 \times$ the upper limit of normal.
- Active pregnancy or breastfeeding.
- Active cigarette or e-cigarette smoker.
- Regular (>2 hours per week) aerobic high-intensity exercise training

Rationale: These criteria ensure a metabolically homogeneous dyslipidaemic cohort without overt cardiovascular disease, while minimizing safety concerns for high-intensity exercise and statin exposure.

23. Recruitment

CONSORT flow will report numbers assessed, randomized, allocated, treated, completed, and analyzed per arm.

24. Withdrawal/Follow-up

Participants who discontinue the intervention will be encouraged to attend the post-intervention (V2) assessments whenever feasible to minimize missing data. Reasons for withdrawal or loss to follow-up will be summarized descriptively by randomization group. All randomized participants will be included in CONSORT flow diagrams and intention-to-treat analyses.

25. Baseline Participant Characteristics

Baseline characteristics will be summarized descriptively for all randomized participants and stratified by randomization group:

1. Exercise + Atorvastatin; 2. Exercise + Placebo; 3. No Exercise + Atorvastatin; 4. No Exercise + Placebo. Unless otherwise specified, summaries will be based on the ITT population.

The distribution of each variable will be inspected visually using Q–Q plots and histograms. Variables with approximately normal distributions will be summarized as mean ± SD; non-normally distributed variables will be reported as median [25th–75th percentiles].

Categorical variables will be reported as counts and percentages.

Table 1 will summarize key demographic, anthropometric, cardiorespiratory, metabolic, biochemical, and patient-reported variables. The final variable list may include but is not limited to the following:

| Variable | Total (n =) | Exercise + Atorvastatin | Exercise + Placebo | No Exercise + Atorvastatin | No Exercise + Placebo |
|--------------------------|-----------------|----------------------------|-----------------------|----------------------------------|--------------------------|
| Demographics | | | | | |
| Sex (M/F) (n (%)) | | | | | |
| Age (years) | | | | | |
| Anthropometry | | | | | |
| Height cm | | | | | |
| Weight kg | | | | | |
| BMI kg·m ⁻² | | | | | |
| Waist circumference (cm) | | | | | |
| Hip circumference (cm) | | | | | |
| Body fat (%) | | | | | |
| Lean mass (kg) | | | | | |

| | | | | | |
|--|--|--|--|--|--|
| Cardiorespiratory | | | | | |
| VO _{2peak} (mL·min ⁻¹) | | | | | |
| VO _{2peak} (mL·kg ⁻¹ ·min ⁻¹) | | | | | |
| Resting heart rate (BPM) | | | | | |
| Systolic BP (mmHg) | | | | | |
| Diastolic BP (mmHg) | | | | | |
| Metabolic profile | | | | | |
| Fasting glucose (mmol/L) | | | | | |
| HbA _{1c} (mmol/mol) | | | | | |
| Fasting insulin (pmol/L) | | | | | |
| Fasting c-peptide (pmol/L) | | | | | |
| HOMA-IR | | | | | |
| Lipids (total, LDL, HDL, TG) mmol/L | | | | | |
| Apolipoproteins (A-I, A-II, B etc.) | | | | | |
| Muscle biochemistry | | | | | |
| Citrate synthase activity ($\mu\text{mol}\cdot\text{g}^{-1}\cdot\text{min}^{-1}$) | | | | | |
| 3-HAD activity ($\mu\text{mol}\cdot\text{g}^{-1}\cdot\text{min}^{-1}$) | | | | | |
| PFK activity ($\mu\text{mol}\cdot\text{g}^{-1}\cdot\text{min}^{-1}$) | | | | | |
| Clinical and patient- reported | | | | | |

| | | | | | |
|------------------------------|--|--|--|--|--|
| SF-36 (total and subdomains) | | | | | |
| SAMS scores (0–10) | | | | | |

Section 6: Analysis

26. Outcome definitions

Primary outcome

- *Citrate-synthase maximal activity* ($\mu\text{mol}\cdot\text{g}^{-1}\cdot\text{min}^{-1}$), measured in skeletal-muscle homogenates by fluorometry.

The primary endpoint is the change from baseline (V1) to 12-week follow-up (V2).

Key secondary outcome

- *Maximal oxygen uptake (VO_{2peak})* ($\text{mL}\cdot\text{kg}^{-1}\cdot\text{min}^{-1}$), assessed during an incremental cycling test to exhaustion.

The key secondary endpoint is the change from V1 to V2.

Additional secondary outcomes

Unless otherwise specified, outcomes refer to the within-participant change (V2 – V1).

They include (but are not limited to) variables in the following domains:

1. **Cardiorespiratory and hemodynamic:** VO_{2peak} (absolute), steady-state VO_2 , resting HR, systolic and diastolic BP.
2. **Body composition and anthropometry:** body weight, fat %, lean mass (BIA), waist/hip circumference.
3. **Lipid and lipoprotein profile:** total, LDL, HDL, triglycerides, lipoprotein(a), apolipoproteins (A-I, B-100 etc.), CETP, LCAT, albumin, transthyretin.
4. **Glucose metabolism and insulin sensitivity:** fasting glucose, insulin, HbA_{1c} , HOMA-IR, Matsuda index, ISR, oral disposition index.

5. **Muscle biochemistry and mitochondrial function:** 3-HAD, PFK, CoQ10, intramuscular atorvastatin (CoQ10 and intramuscular atorvastatin will be quantified only where sufficient muscle tissue is available after primary analyses).
6. **Patient-reported outcomes:** SF-36 (total + subdomains), SAMS (severity & type).
7. **Exploratory outcomes:** anaerobic capacity (Wingate), systemic biomarkers (CoQ10, CRP, cytokines), white-blood-cell count, telomere length, PFAS, hemoglobin mass (CO-rebreathing), targeted / untargeted muscle proteomics, RPE (training/testing).

Note: Detailed laboratory and assay procedures (e.g., DIA-PASEF, UHPLC-MS) are specified in the main protocol. Outcome definitions may be refined based on data quality and scientific relevance before database lock.

27. Analysis method

Analyses will primarily follow the intention-to-treat (ITT) principle (see Section 20), with complementary per-protocol (PP) analyses assessing efficacy under adherence conditions.

Primary Analysis

All continuous outcomes will be analyzed using constrained mixed models, with inherent baseline adjustment (all participants will be put in the same group at baseline). The model will include group (four arms), time (V1/V2; categorical), group × time interaction, sex (male/female), and prior active statin treatment (yes/no) as fixed effects and will be specified with an unstructured covariance pattern to account for repeated measurements on each participant and use the Satterthwaite approximation for degrees of freedom. Model residuals and fitted values will be inspected, and right-skewed outcomes may be log-transformed.

Supplementary analysis

- **Per-protocol analysis:** conducted in the predefined PP population (see Section 20) to estimate efficacy under adherence conditions.
-

28. Handling Missing Data

Missingness may occur due to withdrawal, assay failure, or QC exclusion.

Analyses will assume that outcome data are missing at random (MAR) conditional on observed data included in the analysis model. Missing data will be handled implicitly in the constrained mixed model using maximum likelihood estimation. The extent and reasons for missingness will be summarized by group.

Sensitivity analyses

Sensitivity analyses for the primary outcome (CS activity) and the pre-specified secondary outcome (VO_{2peak}) may be conducted if dropout exceeds 10% in any randomization group to assess robustness to missing-data assumptions. In such cases, simple plausibility-bound scenarios may be applied (e.g., baseline value carried forward). These analyses are intended as plausibility bounds rather than definitive MNAR analyses; confirmatory inference for ΔCS will remain based on the prespecified LMM under the MAR assumption; VO_{2peak} sensitivity results will be interpreted descriptively.

29. Additional analyses (supportive/exploratory)

